4.3. Restrictions

Subjects must abstain from the use of alcohol and from consuming grapefruit, Seville oranges, star fruit, or grapefruit containing products from diet at least 14 days prior to the 1st dose and for the duration of the study. Excluded medications are described in Section 5.4.

4.4. Reproductive Potential

4.4.1. Contraception

Sexually active females of childbearing potential should be using a medically acceptable form of birth control. Females of childbearing potential must be advised to use medically acceptable birth control throughout the study period and for 30 days after the last dose of IP. If hormonal contraceptives are used, they should be administered per the package insert.

Females of childbearing potential who are not currently sexually active, but who become sexually active during the period of the study and 30 days after the last dose of IP must agree to use acceptable contraception, as defined below:

- Premenarchal and either Tanner stage 1 or < 9 years or age, *or*
- Surgically sterile (having undergone 1 of the following surgical acts: hysterectomy, bilateral tubal ligation, bilateral oophorectomy, or bilateral salpingectomy) and at least 8 weeks' post-sterilization, *or*
- Females of childbearing potential must have a negative serum pregnancy test prior to taking the first dose of IP and must agree to abstain from sexual activity that could result in pregnancy or agree to use a medically acceptable method of birth control.

- Abstinence is an acceptable method of birth control only if this is in line with the preferred and usual lifestyle of the subject. Periodic abstinence (e.g., calendar, ovulation, symptothermal, post-ovulation methods) and withdrawal are not acceptable methods of contraception.
- Medically acceptable methods of birth control include:
 - a. Intrauterine device plus condoms
 - b. Double-barrier methods (eg, condoms and diaphragm with spermicidal gel or foam)
 - c. Hormonal contraceptives (oral, patch, injectable, or vaginal ring), stabilized for at least 1 month prior to screening visit, plus condoms. Note: If a subject becomes sexually active during the study, she should use 1 of the other acceptable methods noted above in addition to the hormonal contraceptive until it has been stabilized for 30 days prior to screening visit.

4.5. Discontinuation of Subjects

A subject may withdraw — or their parent/LAR may withdraw the subject — from the study at any time for any reason without prejudice to their future medical care by the physician or at the hospital. The PI or sponsor may withdraw the subject at any time (eg, in the interest of subject safety). The PI is encouraged to discuss withdrawal of a subject from IP with the medical monitor when possible.

Subjects who discontinue IP treatment before the completion of the DB phase will continue to be followed per protocol and, at a minimum, subjects will be encouraged to maintain daily seizure eDiary entries until the DB phase is completed. These subjects should also return to the site after the taper for safety follow-up post taper assessments (Section 7.2.7).

If the IP is discontinued at any time, subjects should follow the 2-week taper schedule, unless otherwise medically indicated (Section 7.2.6). If the subject discontinues during the OL phase, evaluations listed for the Taper Visit are to be performed as completely as possible. Whenever possible, all subjects who discontinue should also undergo the protocol-specified Safety Follow-up Post-Taper visit (Section 7.2.7). Comments (spontaneous or elicited) or complaints made by the subject must be recorded in the source documents. The reason for termination, date of stopping IP, and total amount of IP taken must be recorded in the electronic case report form (eCRF) and source documents. Discontinuation of IP due to AEs must also be reflected on the AE eCRF page.

4.5.1. Subject Withdrawal Criteria

All subjects or her parent/LAR reserve the right to withdraw from the clinical study at any time, as stated in the informed consent/assent form. The PI may discontinue subjects from the clinical study for any of the following reasons:

- Subject is found to have entered the study in violation of the protocol;
- Subject requires the use of a disallowed concomitant medication;
- Subject's condition changes after entering the clinical investigation so that the subject no longer meets the inclusion criteria or develops any of the exclusion criteria;

- Subject or parent/LAR withdraws consent or assent to participate in the study;
- Subject is noncompliant with the procedures set forth in the protocol;
- Subject experiences an AE/SAE that warrants withdrawal from the study;
- It is the PI's opinion that it is not in the subject's best interest to continue in the study;
- Subject has an AST or ALT increase $> 3 \times$ upper limit of normal (ULN) during the study.
NOTE: If this occurs, the subject should be followed with weekly laboratory repeat testing and continue in the study if levels are trending down. Discontinuation of treatment should be considered if levels do not decline to under $3 \times$ ULN and if presented with the appearance of fatigue, nausea, vomiting, right upper quadrant pain or tenderness, fever, rash, and/or eosinophilia ($>5\%$) and if there are no initial findings of cholestasis (elevated serum ALP) or other reason can be found to explain the combination of increased ALT or AST and total bilirubin, such as viral hepatitis A, B, or C; preexisting or acute liver disease; or another drug capable of causing the observed injury; or
- Subject has a total bilirubin increase to $1.5 \times$ ULN or more during study. **NOTE:** if this occurs, the subject should be followed with weekly laboratory repeat testing and continue in the study if levels are trending down. Discontinuation of treatment should be considered if levels do not decline to under $1.5 \times$ ULN within the time period that is considered reasonably safe per PIs' judgment. Laboratory, medical, or clinical finding for which clinical intervention should take precedence over study participation.

Decisions to discontinue the study will be made at each participating site by the PI. If feasible, the reason for discontinuation should be discussed with the sponsor's medical monitor prior to subject discontinuation. Subjects who discontinue IP during the DB phase will continue to record daily seizure frequency at minimum until the completion of the DB phase.

If a subject must be abruptly discontinued from the investigational product (e.g., severe rash), careful attention should be paid for the possibility of withdrawal symptoms such as increase in seizure number or severity. Consideration should be made by the investigator for providing another GABA_A receptor modulator medication for 1-2 weeks such as clobazam to mitigate the potential risk of withdrawal from a positive modulator of GABA_A receptors.

4.5.2. Reasons for Early Discontinuation

The reason for early discontinuation must be determined by the PI and recorded in the subject's source documents and on the eCRF. If a subject is withdrawn for more than 1 reason, each reason should be documented in the source document and the most clinically relevant reason should be entered on the eCRF.

Reasons for early termination include but are not limited to the following:

- Adverse event in which the character, severity or frequency is new in comparison to the subject's existing risk profile with the exception of somnolence and seizures.
- An Adverse Event that is associated with non-reversible target organ dysfunction, with the associated laboratory abnormalities as defined in exclusion criteria 11, 12 or 13. An allowance may be made for continued treatment if the abnormality is not medically

significant (non-life-threatening or does not require ongoing treatment that could be life-threatening)

- A laboratory abnormality or vital sign change that is irreversible and considered medically significant, associated with use of the investigational product
- Protocol violation/protocol deviation
- Withdrawal by subject or parent/LAR
- Lost to follow-up
- Lack of efficacy
- Death
- Physician decision
- Other (must be specified in the subject source document and eCRF)
- Pregnancy

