9. Have an active CNS infection, demyelinating disease, degenerative neurological disease, or CNS disease deemed progressive as evaluated by brain imaging (magnetic resonance imaging [MRI]).
10. Have any disease or condition (medical or surgical; other than PCDH19-related epilepsy) at the screening visit that might compromise the hematologic, cardiovascular, pulmonary, renal, gastrointestinal, or hepatic systems; or other conditions that might interfere with the absorption, distribution, metabolism, or excretion of the investigational product, or would place the subject at increased risk.
11. An aspartate aminotransferase (AST/serum glutamic oxaloacetic transaminase [SGOT]) or alanine aminotransferase (ALT/serum glutamic pyruvic transaminase [SGPT]) $> 3 \times$ the upper limit of normal (ULN) at screening and if applicable confirmed by a repeat test. If the subject has another reason to be excluded, repeated liver enzymes are not required.
12. Total bilirubin levels $> 1.5 \times$ ULN at screening and if applicable confirmed by a repeat test. In cases of documented, stable medical condition (i.e., Gilbert's Syndrome) resulting in levels of total bilirubin $>$ ULN, the medical monitor can determine if a protocol exception can be made.
13. Subjects with significant renal insufficiency, estimated glomerular filtration rate (eGFR) < 30 mL/min (calculated using the Cockcroft-Gault formula or Pediatric GFR calculator or Bedside Schwartz), will be excluded from study entry or will be discontinued if the criterion is met post baseline.

- 14. Have been exposed to any other investigational drug within 30 days or fewer than 5 half-lives prior to the screening visit.
- 15. Unwillingness to withhold grapefruit, Seville oranges, star fruit, or grapefruit-containing products from diet 14 days prior to 1st dose and for the duration of the study
- 16. Unwillingness to withhold alcohol throughout the entire clinical trial.
- 17. Have active suicidal plan/intent or have had active suicidal thoughts in the past 6 months or a suicide attempt in the past 3 years.
- 18. Known sensitivity or allergy to any component in the investigational product(s), progesterone or other related steroid compounds.

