11. An aspartate aminotransferase (AST/serum glutamic oxaloacetic transaminase [SGOT]) or alanine aminotransferase (ALT/serum glutamic pyruvic transaminase [SGPT]) $> 3 \times$ the upper limit of normal (ULN) at screening and if applicable, confirmed by a repeat test. If the subject has another reason to be excluded, repeated liver enzymes are not required.

12. Total bilirubin levels $> 1.5 \times \text{ULN}$ at screening and if applicable, confirmed by a repeat test. In cases of documented, stable medical condition (i.e., Gilbert's Syndrome) resulting in levels of total bilirubin $> \text{ULN}$, the medical monitor can determine if a protocol exception can be made.
13. Subjects with significant renal insufficiency, estimated glomerular filtration rate (eGFR) $< 30 \text{ mL/min}$ (calculated using the Cockcroft-Gault formula or Pediatric GFR calculator or Bedside Schwartz), will be excluded from study entry or will be discontinued if the criterion is met post baseline.
14. Have been exposed to any other investigational drug within 30 days or fewer than 5 half-lives prior to the screening visit.
15. Unwillingness to withhold grapefruit, Seville oranges, star fruit, or grapefruit containing products from diet 14 days prior to 1st dose and for the duration of the study
16. Unwillingness to withhold alcohol throughout the entire clinical trial.
17. Have active suicidal plan/intent or have had active suicidal thoughts in the past 6 months or a suicide attempt in the past 3 years.
18. Known sensitivity or allergy to any component in the IP(s), progesterone or other related steroid compounds.

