7.6.5. Clinical Laboratory Tests

Clinical laboratory tests are listed in Section 12.2 and will be collected per the schedules listed in Table 1 and Table 2. If any test result is unexpectedly out of range, a repeat test can be performed at any time as decided by the PI to confirm the initial result.

The following liver function and eGFR tests will be monitored throughout the study as follows.

- If AST or ALT increases > 3 times ULN during the study, subject should be followed with weekly laboratory repeat testing and continue in study if levels trending down. Subject will be discontinued if levels do not decline to under $3 \times$ ULN.
- If total bilirubin increases to $1.5 \times$ ULN or more during study, the subject will be discontinued.
- Subjects with significant renal insufficiency, eGFR < 30 mL/min (calculated using the Cockcroft-Gault formula), will be discontinued if the criterion is met post baseline.

If any of the criteria above are deemed clinically significant by the PI, then the sponsor's medical monitor should be contacted.

Due to the difficulty in obtaining urine samples, urinalysis will be conducted as follows: during the DB phase at Visit 1 (screening) or baseline/randomization (Visit 2), Visit 3, and at Week 17 (Visit 5; also Final DB Visit/First OL Visit in OL phase); in the OL phase at Visit 7 (Week 36), Visit 8 (Week 52) and annually thereafter, or at the Safety Follow-up Post-Taper visit if IP is discontinued; and at the Final OL Visit. An attempt will be made to collect a urine sample at screening to perform the study-related urinalysis. Otherwise, the urine sample for the urinalysis can be collected at baseline.

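### Section 4.5.2 lets treatment continue at an eGFR below 30 mL/min, where exclusion criterion 13 and Section 7.6.5 require discontinuation

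*Protocol*

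**What the plan says.** Protocol Section 4.5.2 lists reasons for early termination. One is an adverse event tied to non-reversible dysfunction of a target organ, "with the associated laboratory abnormalities as defined in exclusion criteria 11, 12 or 13". The same bullet goes on: "An allowance may be made for continued treatment if the abnormality is not medically" significant, which it explains in brackets as "non-life-threatening or does not require ongoing treatment that could be life-threatening".

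Exclusion criterion 13, in the Synopsis and in Section 4.2, concerns an eGFR below 30 mL/min. It opens "Subjects with significant renal insufficiency" and says that such subjects "will be excluded from study entry or will be discontinued if the criterion is met post baseline". Section 7.6.5, on laboratory monitoring, gives the same threshold and says that these subjects "will be discontinued if the criterion is met post baseline". Footnote c of Protocol Appendix 2 (Section 12.2) and footnote c of SAP Section 14.2.1 repeat the Section 7.6.5 rule.

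Section 4.5.1 lists grounds on which the investigator may discontinue a subject. Developing any exclusion criterion during the study is one of them. The eGFR rule is not mentioned there.

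**The concern.** The allowance in 4.5.2 names criterion 13 expressly, so it reaches an eGFR below 30 mL/min. Criterion 13 and Section 7.6.5 treat that value as ending treatment. One text permits continued dosing and the other forbids it, for the same child with the same result, and no order of precedence is stated.

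What is at stake is the clarity of a safety stopping rule. The subjects are aged 1 to 17 years, and Section 3.4 foresees open-label drug for three additional years or more, so the rule matters long after enrollment closed. Section 4.5.1 leaves discontinuation decisions to the investigator at each site, with prior discussion with the medical monitor only if feasible. Investigators therefore need a rule that can be read in only one way.

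**Working it through.** No arithmetic applies. The only number is the threshold of 30 mL/min, which is the same wherever it is stated. The check is a comparison of current text; nothing rests on the summary of changes.

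| Place | Trigger | Instruction |
|---|---|---|
| Protocol 4.5.2 | Adverse event, non-reversible organ dysfunction, abnormality of criterion 11, 12 or 13 | Treatment may continue if the abnormality is judged not medically significant |
| Protocol 4.5.1 | Any exclusion criterion develops | Investigator may discontinue |
| Synopsis and Protocol 4.2, criterion 13 | eGFR below 30 mL/min after baseline | Discontinuation required |
| Protocol 7.6.5 | Same | Discontinuation required |
| Protocol Appendix 2, footnote c | Same | Discontinuation required |
| SAP 14.2.1, footnote c | Same | Discontinuation required |

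1. *Is the cross-reference in 4.5.2 stale?* No. In the current Section 4.2, criteria 11, 12 and 13 are AST/ALT, total bilirubin and eGFR: the laboratory criteria one would expect that bullet to mean.

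2. *Do the triggers overlap?* Yes. A child with a renal adverse event, non-reversible dysfunction and an eGFR below 30 mL/min meets the 4.5.2 bullet. She also meets criterion 13 and the 7.6.5 rule, both of which apply with or without an adverse event.

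3. *Does 7.6.5 contain an exception that would reconcile the texts?* It has two qualifying sentences. One says that "a repeat test can be performed at any time as decided by the PI to confirm the initial result"; that verifies the value and does not permit dosing to continue once the value stands. The other reads "If any of the criteria above are deemed clinically significant by the PI, then the sponsor's medical monitor should be contacted"; that is a duty to notify, not a permission to continue. Criterion 13 and the two footnotes have no qualification.

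4. *Does another section settle the matter?* Section 4.5 lets the investigator or sponsor withdraw a subject at any time. That permits stopping but does not require it. Section 4.5.1 is likewise permissive for a subject who develops an exclusion criterion. No section gives an order of precedence.

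5. *Does the meaning of discontinued matter?* The mandatory texts do not say whether they mean study drug or the study. Either meaning is incompatible with continued treatment.

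An eGFR below 30 mL/min therefore falls under a permission in 4.5.2, a discretion in 4.5.1 and a requirement in the other places.

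**The case against.** The strongest reply is that the texts can be reconciled. The allowance is permissive, sits in one bullet of an open-ended list of reasons to be recorded, and does not say that it waives criterion 13 or Section 7.6.5. A rule written for eGFR alone would ordinarily prevail over an allowance written for three criteria together. On that view all that is missing is a carve-out. This lowers the seriousness but does not remove the conflict: 4.5.2 names criterion 13, and the allowance is an operative permission to treat, not a recording instruction.

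The reply does defeat some stronger claims that a reader might draw. One is that two investigators could handle the same child differently and both comply. They could not: the one who keeps dosing can point to 4.5.2 but still breaches criterion 13 and Section 7.6.5, while the one who stops breaches nothing. Another is that the sicker child is governed by the softer rule. That holds only if the allowance is read as overriding the mandate, which no text says.

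A third tempting reading is that either half of the bracketed explanation is enough, so that any abnormality that is not life-threatening qualifies. The wording allows this. It equally allows the narrower sense that the abnormality must be neither life-threatening nor in need of treatment that could be. The next bullet in 4.5.2, which separately lists irreversible and medically significant laboratory changes associated with study drug, shows that the section does not treat all such abnormalities leniently. The point does not depend on this reading, since on either one the decision at this eGFR is left to judgement.

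Finally, the documents do not show whether the sponsor meant the allowance to soften the eGFR rule. Resolving the conflict towards the stricter text is a choice made here on safety grounds.

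**Conclusion.** The contradiction is real and in current text, but narrow. For criterion 13 only, 4.5.2 permits what criterion 13 and Section 7.6.5 forbid, and 4.5.1 adds a further permissive wording. The consequence is that an investigator has protocol text to cite for continuing a child who must be discontinued; it is not that continuing would be compliant.

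The case is expected to be rare. About 25 subjects were expected to be randomized, and the documents give no rate for an eGFR below 30 mL/min, so none is assumed. No effect on the efficacy analysis is claimed. The number of places that state the mandatory rule adds little weight, because they restate essentially one rule.

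The conclusion rests on two things: that the cross-reference to criterion 13 in 4.5.2 means what it says, and that no precedence rule exists elsewhere in the documents. It does not extend to AST/ALT or bilirubin. The allowance covers criteria 11 and 12 too, but their monitoring rules raise separate questions. The change should be made because it is cheap and the rule protects children.

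**What to change.** In Protocol Section 4.5.2, add after the allowance: *This allowance does not apply to exclusion criterion 13; a subject who meets criterion 13 post baseline will be discontinued from study drug.* Naming study drug keeps the follow-up that Section 4.5 asks for after early discontinuation in the double-blind phase.

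In Section 4.5.1, add that discontinuation is mandatory, not discretionary, when criterion 13 is met.

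Leave the AST/ALT and bilirubin rules, the eGFR formulas and the repeat-test provision as they are. In particular, the new sentence should refer to criterion 13 and not to Section 7.6.5: criterion 13 accepts three ways of calculating eGFR and Section 7.6.5 names only Cockcroft-Gault, and a reference to 7.6.5 would also draw in the liver tests.

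The cost is one sentence in 4.5.2 and a short addition to 4.5.1. No SAP change, new procedure or new data are needed.

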4.5.3. Subjects Lost to Follow-up Prior to Last Scheduled Visit

A minimum of 3 documented attempts must be made to contact any subject lost to follow-up at any time point prior to the last scheduled contact (office visit or telephone contact). At least 1 of these documented attempts must include a written communication sent to the subject's last known address via courier or mail (with an acknowledgment of receipt request) asking that she return to the site for final safety evaluations and return any unused IP. If contact is made but the subject refuses or is unable to return to the site for the final Safety Follow-up Post-Taper visit (Section 7.2.7), it should be documented in the eCRF.

4.6. Subject Numbering

During the screening visit and after consent is obtained, each subject will be assigned a unique 6-digit subject number by the IWRS. The subject number will consist of a 3-digit clinical investigational site number assigned by the sponsor, followed by a 3-digit subject number (eg, 001) assigned by the IWRS. This subject number will also serve as the screening number. A separate randomization number will be assigned once the subject is randomized, but the randomization number will not be used to track the subject. The unique 6-digit subject number will serve as the subject number and be used to track the subject throughout the study. Each randomized subject's number will correspond with a treatment (active or PBO) as determined by the randomization schedule.

The clinical site is responsible for maintaining a current log of subject number assignments and bottle numbers of the IP administered to each subject. The unique subject number is required to be entered on all clinical investigation documentation (eCRFs, labeling of clinical materials and samples containers, drug accountability logs, etc.).

